12.2 CONFIDENTIALITY

12.2.1 ACCESS TO SOURCE DOCUMENTS

The research coordinator, research assistants, and PI will have access to all of the source documents collected over the course of the study. The Co-I and medical monitor will have access to files upon request, as they will need access to the locked rooms and filing cabinets in which these documents are located.

Data will stay on a password-protected computer. Subsequently, a copy will be processed on a separate, password-protected desktop computer in the [name] Lab (Neuroscience Research Building 4129).

12.2.3 OTHER

Please note that there is no significant risk of deductive disclosure in this study. In addition, none of the groupings or subgroupings used in analysis will be small enough to allow individuals to be identified.

12.3 SOURCE DOCUMENTS

Source data is all information, original records of clinical findings, observations, or other activities in a study necessary for the reconstruction and evaluation of the trial. Source data are contained in source documents. Source data include:

PARTNERS HUMAN RESEARCH COMMITTEE (IRB).

- All IRB correspondences are documented
- The study staff is IRB approved prior to performing any study procedures
- All versions of the IRB protocols and informed consent forms are on file

INFORMED CONSENT.

- Ensure that participant identification is not recorded on the ICF (i.e., no participant ID)
- There is documentation that the participant is given a copy of the consent form
- The participant and study representative signed and dated the consent form for him/herself
- The participant initialed and dated all appropriate pages on the informed consent form
- Note to file (Appendix D) made for any informed consent deviations
- Ensure a valid (current version date) copy of the consent form was used

PROTOCOL DEVIATIONS.

- Any and all protocol deviations (exceptions and violations) are documented in the participant folder and reported to the IRB as required

OTHER SOURCE DOCUMENTS.

- Each participant folder will contain a checklist to ensure that all source documents are administered and collected properly. The checklist will be dated by the researcher for each time an assessment is administered
- Review participant folders to ensure the accuracy, completeness, and legibility of the data.
- Any correction made to the source documents is dated, initialed, and explained. The original entry should not be obscured.
- The protocol-specific source documents are on file.
- Source documents are completed in ink.
- Note to files (Appendix D) are made for missing or incomplete data and to explain any discrepancies or additional comments.

12.4 DATA MANAGEMENT RESPONSIBILITIES

The responsibilities designated to each member of the research team are documented on the Delegation of Authority Form. The study coordinator and research assistants will be responsible for the informed consent process, review for eligibility, questionnaire administration, data entry, device administration, EEG administration, and CRF entries. The study coordinator will be responsible for documentation and reporting, while the PI will be responsible for review of the documentation forms, and overview of the research staff.

12.5 DATA CAPTURE METHODS (REDCAP)

All data will be entered into a data capture system provided by REDCap. The data system includes password protection and internal quality checks, such as automatic range checks, to identify data that appear inconsistent, incomplete, or inaccurate. Clinical data will be entered directly from the source documents.

All assessments completed by the participant at home will be completed via REDCap as well, ensuring participant security and confidentiality.

12.6 PROTOCOL DEVIATIONS

All deviations from the protocol will be addressed in study participant source documents. The researcher will complete a Protocol Deviation Log using the participant code as the identifier. This form will collect information such as the date the deviation occurred, details of what the deviation consisted of, any corrective and preventative actions that were taken as a result of the deviation, and the date that the PI and IRB were notified. The PI will

review the information and initial once approved. A completed copy of the Protocol Deviation Form will be maintained in the regulatory file, as well as in the participant's source document. Protocol deviations will be sent to the IRB per their guidelines. The site PI/study staff will be responsible for knowing and adhering to their IRB requirements.

12.7 RECORD RETENTION

According to the University of North Carolina at Chapel Hill's Archives and Record Management Services schedule for General Records Retention and Disposition Schedule 6.10, records will be kept for 5 years after the completion of the study or grant end date, whichever is later.

13 ETHICAL CONSIDERATIONS

13.1 ETHICAL STANDARD

The investigator will ensure that this study is conducted in full conformity with the principles set forth in the Belmont Report: Ethical Principles and Guidelines for the Protection of Human Subjects of Research, as drafted by the US National Commission for the Protection of Human Subjects of Biomedical and Behavioral Research (April 18, 1979) and codified in 45 CFR Part 46 and/or the ICH E6; 62 Federal Regulations 25691 (1997).

13.2 INSTITUTIONAL REVIEW BOARD (IRB)

The Office of Human Research Ethics is responsible for ethical and regulatory oversight of research at UNC-Chapel Hill that involves human participants. The OHRE administers, supports, and guides the work of the Institutional Review Boards and all related activities. Any research involving human participants proposed by faculty, staff, or students must be reviewed and approved by an IRB before research may begin, and before related grants may be funded. OHRE and the IRBs are critical components of the coordinated Human Research Protection Program, which serves to protect the rights and welfare of human participants. All components of this program must work together to ensure institutional compliance with ethical principles and regulatory requirements. The following is a mission statement for the coordinated Human Research Protection Program:

The University of North Carolina at Chapel Hill is committed to expanding and disseminating knowledge for the benefit of the people of North Carolina and the world. An important part of that commitment to knowledge is research of the highest quality on all aspects of the health and behavior of people, and such research is only possible through the participation of humans as research participants. Human participants are partners in research and a precious resource to the university. At UNC-Chapel Hill, human participant research is a privilege, but not a right. Consistent with that philosophy, it is the mission of the UNC-Chapel Hill Human Research Protection Program to ensure that:

- a. The rights and welfare of human participants are paramount in the research process;
- b. The highest standards of ethical conduct are employed in all research involving human participants;
- c. Research investigators are properly trained in the ethical and regulatory aspects of research with human participants;
- d. Research investigators deal honestly and fairly with human participants, informing them fully of procedures to be followed, and the risks and benefits of participating in research; and
- e. Research using human participants at UNC-CH conforms to applicable local, state, and federal laws and regulations and the policies of the university.

13.3 INFORMED CONSENT PROCESS

Informed consent is a process that is initiated prior to the individual's agreeing to participate in the study and continues throughout the individual's study participation. Extensive discussion of risks of TMS and GTT will be provided to the participants. Consent forms describing, in detail, the study intervention, device, procedures, and risks are given to the participant and written documentation of informed consent is required prior to the administration of any assessments used in this study. All consent forms will be IRB-approved and updated with any new information as modifications are made throughout the study.

Together, the researcher and potential participants will review the study in its entirety by reviewing the consent form together in a private location. At several intervals during the consent review, the researcher will ask the

participant questions that will assess the comprehension of the information in the consent. If the participant is unsure or does not know, the researcher will return to that section and more carefully explain the information. Participants must sign the informed consent document prior to any procedures taking place. If needed, the participants will have the opportunity to discuss the study with their surrogates or think about it prior to agreeing to participate. Participants may withdraw consent at any time throughout the course of the trial. A copy of the informed consent document will be given to the participants for their records.

13.4 EXCLUSION OF WOMEN, MINORITIES, AND CHILDREN (SPECIAL POPULATIONS)

Non-English speaking individuals are excluded because the ability to accurately and complete communicate study information, answer questions about the study, and obtain consent is necessary.

13.5 PARTICIPANT CONFIDENTIALITY

Participant confidentiality is strictly held in trust by the participating investigators, their staff, and the research team. This confidentiality is extended to cover testing of biological samples and genetic tests in addition to the clinical information relating to participants.

All data will only be referenced by dummy identifier code. Data will be stored on a password protected computer. A key connecting names and code numbers will be kept in a locked cabinet, accessible only by research personnel. All data will be stored and analyzed on password protected computers, also only accessible by research personnel. Participants will not be identified in any report or publication about this study. See *10 Data Handling and Record Keeping* for more information on source documentation storage and security.

13.6 STUDY DISCONTINUATION

In the event that the study is discontinued, participants who have completed or who are still enrolled in the study will be notified. Any new information gained during the course of the study that might affect participant's willingness to continue will be communicated within 2 days of the PI learning this information.

14 PUBLICATION POLICY

There are no restrictions on publications since this is an investigator-initiated study funded by a grant agency that has no influence on the publications resulting from this study.

APPENDIX A: SCHEDULE OF EVENTS

A detailed schematic describing phone screening and study visits.

Procedures	Phone Screening	On-Site Screening	Study Sessions
Provide Verbal Consent	x		
Signed Consent Form		x	
Assessment of Eligibility Criteria	x	x	
Review of Medical History	x	x	
Review of Concomitant Medications	x	x	
Behavioral and Mood Questionnaires		x	x
Glucose Drink Administration			x
Capillary blood sampling (finger prick)			x
Non-Invasive Brain Stimulation			x
Side-Effects Questionnaires			x

APPENDIX E: TELEPHONE SCRIPT

Hello, my name is _____ and I am a _____ from the University of North Carolina at Chapel Hill conducting a research study about investigation of blood glucose level and neuronal excitability. Based on your history, you may be eligible to participate in our study.

Do you have time now to hear about the study, answer a few screening questions?

(If 'No', ask for a good time to call back)

(If 'Yes', proceed)

Great! This study is investigating how changes in blood glucose level modulate neuronal excitability. Findings from this study will help the development of new study. In this study, a very weak electric current will be applied to your scalp. Some people report a tingling, itching because of this stimulation, but no other side effects have been found. It is not a shock and should not cause pain. Also, we will collect your 5uL blood on your finger by pricking to measure your blood glucose level. This procedure is widely used for diagnosing diabetes in hospitals thus there is no other side effects for blood sampling.

Participation in this study includes 1 on-site screening visit and 2 study sessions. You will be compensated for your time spent participating in the study. The maximum compensation for this study is \$200 for completing all sessions. Are you still interested in participating?

(If 'No', thank them for their time; if 'Yes', proceed)

Great! In order to make sure you're eligible for the study, I need to ask you a few questions. Please answer yes or no. You do not need to provide any further details.

(If the answer given is not the same as the answer shown, thank the individual for his or her interest and say, unfortunately, they do not qualify for the current study)

- Are you between 35 to 65 years old and right-handed? (Yes)
- Have you ever, or are you currently being diagnosed with diabetes and pre-diabetes?
- Have you ever, or are you currently being treated for a neurological condition (e.g., epilepsy, migraines)? (No)
- Are you currently taking medication for any other psychiatric illness? (No)
- Have you ever had brain surgery? (No)
- Do you have any brain devices or implants, including a cochlear implant or aneurysm clip? (No)
- Have you ever been diagnosed with a traumatic brain injury? (No)

Phone Screening:

- Pass
- Fail

Reason for failing: _____

You are eligible for participation in the stimulation session of the study.

Scheduled Session

Date: _____

Time: _____

I will send you an email confirming this time, and providing directions on how to find the specific location of your session. We will also send you an email to confirm your appointment 24 hours beforehand. Please respond to this email so we know you are still coming. If you have any questions before then, please don't hesitate to contact us at this phone number or at [contact]. Thank you for your time.

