Description of Intervention (Procedures/methods)	Each participant will be seated in a reclining chair and receive transcranial magnetic stimulation (TMS) to determine resting motor threshold (RMT). At baseline, participants will receive 10 TMS pulses (120% intensity relative to RMT) while wearing an electroencephalography (EEG) net to record brain activity on the scalp. TMS-induced motor-evoked potentials (MEPs) and EEG data will be recorded. In addition, blood glucose level testing will be performed by finger prick to measure baseline glucose level. In an intervention step, glucose drink (75g of sugar) or drinking water (control condition) will be administered. Both blood glucose level testing and TMS-induced MEPs and EEG data collection will be performed at 0, 30, 60, 120, and 180 minutes after drink administration.
Related IRB Applications	17-0149

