2.1 BACKGROUND

More than a third of the adult US population has impaired glucose tolerance, which is tightly linked to obesity and a risk factor for the development of diabetes and disorders of the central nervous system. In particular, diabetes exhibits a bidirectional causal association with depression. A growing literature delineates the pathophysiology underlying mood disorders at the level of large-scale activity patterns in brain circuits (Davidson, 1985; Nusslock et al., 2015; Smart et al., 2015; Sutton and Davidson, 1997), which has enabled the development of novel brain stimulation treatments such as transcranial magnetic stimulation (TMS) (George et al., 1995). TMS is one of the non-invasive brain stimulation tools used to deliver electrical stimuli through the scalp in humans. In general, single-pulse TMS (including paired-pulse TMS) is used to explore brain functioning. TMS on the motor cortex leads to a twitch in the target muscle evoking motor-evoked potentials (MEPs) on electromyography (EMG) electrodes. The MEP is usually used to assess corticospinal tract excitability (Tofts, 1990). In addition, combining TMS with electroencephalography (EEG) can capture cortical excitability beyond corticospinal excitability since EEG mainly captures neural activity of cortical neurons (Farzan et al., 2016). The concurrent combination of TMS with EEG can be a powerful technology for characterizing and modulating brain networks.

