5.1 SCREENING

- Phone screening

The phone screening allows researchers to screen out participants based on self-report responses and for potential participants to become familiar with the study schedule, including procedures. During the telephone screening, researchers will provide a brief background about GTT, TMS, and EEG. The timeline will be explained to the participants and the participant will be informed of compensation, both amount and payment schedule. The participant will be asked if they have any questions. Once all questions have been answered, the participant will be asked if he/she is still interested in participating in the study. If yes, the researcher will ask if the participant will provide verbal consent to begin the initial phone screening which will determine eligibility for the stimulation session. A telephone script, which includes the screening questions, is provided in *Appendix E*.

- Screening visit (Visit 1)

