Single-pulse TMS on the motor cortex leads to a twitch in the target muscle evoking a motor-evoked potential (MEP) measured by electromyography (EMG) electrodes. Participants will be seated in a comfortable armchair with their hands positioned on the armrest. Two disposable electrodes (15x21mm, Ambu Neuroline) will be placed in a tendon-belly arrangement over the first dorsal interosseous muscle and a ground electrode will be placed over the styloid process of the ulna. A figure-eight coil (C-B60, MagVenture) will be used for stimulation and EMG signals will be recorded by an amplifier (MagPro X100, MagVenture). The coil will be placed tangentially over the scalp with the handle pointing backwards and laterally at 45° from the mid-sagittal line. Biphasic TMS pulses will be applied over the motor cortex and the resting motor threshold (RMT) will be defined by the minimum TMS intensity required to evoke MEP of at least 50 uV in 50% of 10 consecutive trials. At baseline, 10 TMS pulses will be applied on the scalp and EEG and EMG data will be collected. At the same time, blood glucose level will be measured by 5uL of finger prick blood sampling as a baseline glucose level. In an intervention step, we will administer a 75g load of glucose drink or drinking water at each study visit. After then, glucose level testing and EMG/EEG data collection will be performed at 0, 30, 60, 120, and 180 minutes after the drink administration. Once participants complete the first study visit, a study coordinator will schedule their next visit with at least 3-day gap.

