8.2.1 PHYSICAL

Risk of Injury and Discomfort: Non-invasive brain stimulation has been used without any reports of serious side-effects for more than a decade and TMS has been cleared for use in the USA by the FDA. The stimulation made nothing to do with electroconvulsive therapy that applies many orders of magnitude higher stimulation current. Some participants report a scalp pain, tingling, burning, or itching on the stimulation site but no other side effects have been noted. In order to monitor these side-effects, we will be administering side effects stimulation questionnaire after each stimulation session to determine whether these effects were experienced. Research personnel present during these sessions will also check in with the participant periodically during the stimulation to see whether they are comfortable. If any side-effect occurs (rated by the participant as stronger than “moderate”) or the participant is experiencing severe discomfort, the stimulation will be immediately stopped.

Risk of Bleeding: The glucose tolerance test is a medical test in which glucose is given and blood samples taken afterward to determine how quickly it is cleared from the blood. The test is usually used to test for diabetes, insulin resistance, impaired beta cell function, and sometimes reactive hypoglycemia and acromegaly, or rarer disorders of carbohydrate metabolism. We strictly follow the medical guidelines using an FDA-cleared device and sampler and blood sampling will be immediately stopped if any unexpected bleeding occurs.

Risk of Glucose Ingestion: The risks associated with glucose ingestion in healthy participants are minimal.

The potential side effects include nausea, sweating, light-headedness, vomiting, bloating, headache, diarrhea, and constipation. Serious side effects from the test are very uncommon.

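### The Appendix E telephone script contradicts the protocol on the stimulation, its side effects, the visits and the drink, and its diabetes item shows no required answer

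*Combined protocol and SAP*

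**What the plan says.** Section 5.1 sets the content of the call: "During the telephone screening, researchers will provide a brief background about GTT, TMS, and EEG". It adds that the timeline is explained and questions are answered, and it points to Appendix E for the script.

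The script in Appendix E describes the intervention in one sentence: "In this study, a very weak electric current will be applied to your scalp". It then mentions tingling and itching, says nothing else has been found, and says the stimulation is not a shock and is not expected to be painful. The only glucose-related procedure it describes is the finger prick. On the schedule it says: "Participation in this study includes 1 on-site screening visit and 2 study sessions".

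Seven screening questions follow, with an instruction to turn away anyone whose answer differs from the one printed beside the question. The second question is: "Have you ever, or are you currently being diagnosed with diabetes and pre-diabetes". No answer is printed after it.

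The body of the protocol describes something else. The Study Summary says: "At baseline, participants will receive 10 TMS pulses (120% intensity relative to RMT"), with EEG recorded at the same time. Section 5.2 says: "Single-pulse TMS on the motor cortex leads to a twitch in the target muscle evoking a motor-evoked potential (MEP"). Section 8.2.1 says: "Some participants report a scalp pain, tingling, burning, or itching on the stimulation site".

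**The concern.** The script is candidate-facing text, and it is the only wording for the call that the protocol supplies. If it is used as printed, a candidate hears of a stimulation technique that the study does not use, is given a shorter list of side effects than the protocol's own, and does not learn of the MRI visit or of the drink that is the study intervention. Someone unwilling to have TMS, an MRI scan or a glucose load would then find out only at the on-site visit. The screening rule also cannot be applied literally to diabetes and pre-diabetes, the first exclusion listed in section 3.2 of a study built on a glucose challenge.

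**Working it through.** No sample-size, power or error-rate figure is involved. The check sets the script beside the protocol, item by item, with two counts.

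1. **Technique.** Script: a very weak current on the scalp; no mention of TMS, magnetic pulses, EEG or a muscle twitch. Protocol: 10 pulses at 120% of resting motor threshold at baseline (Study Summary), with TMS measurements repeated at 0, 30, 60, 120 and 180 minutes after the drink (section 4). Stimulation set above the threshold for a motor response is not described by the script's sentence.

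2. **Side effects.** Script: tingling and itching, nothing further, no pain expected. Section 8.2.1: scalp pain, tingling, burning and itching. The script keeps two of these four and drops scalp pain and burning. Section 10.1 also lists headache and neck pain among the stimulation side effects; that list is a set of effects to ask about, so the direct contradiction is with section 8.2.1. The glucose-ingestion effects in section 8.2.1, such as nausea, vomiting and light-headedness, are also absent because the drink is absent.

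3. **Visits.** Script: 1 screening + 2 sessions = 3. Sections 5.1 and 5.2: 1 screening (Visit 1) + 1 MRI (Visit 2) + 2 sessions (Visits 3 and 4) = 4. The script is one visit short, and the missing one is the MRI. Appendix A, as it can be read, does not show the MRI either, so it does not settle the matter in the script's favour.

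4. **Drink.** Script: not mentioned. Sections 4 and 5.2: a 75 g glucose load in one session and water in the other.

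5. **Answer key.**

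| Screening item | Required answer shown |
|---|---|
| Age and handedness | Yes |
| Diabetes and pre-diabetes | none |
| Neurological condition | No |
| Psychiatric medication | No |
| Brain surgery | No |
| Brain devices or implants | No |
| Traumatic brain injury | No |

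Six of seven items carry a key. The one without it corresponds to an exclusion in section 3.2, and the script's rule has nothing to compare the caller's answer with.

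6. **What follows the call.** Section 5.1 limits the verbal consent to starting the phone screening. Section 13.3 requires written consent, with discussion of TMS and glucose tolerance test risks, before any assessment. Section 5.1 confirms eligibility at Visit 1, including fasting glucose below 95 mg/dL. Section 6.1 includes a diabetes question in its safety questionnaire, although it says only that coordinators will consider using it. Section 4.1 conceals the allocation until the participant is enrolled and ready for baseline. The documents therefore place the full explanation of TMS and glucose risks, and the main eligibility checks, after the call and before allocation.

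**The case against.** Four points can be made for the plan.

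- **The script may not be the whole call.** Section 5.1 separately requires background on all three procedures and describes Appendix E as a script that includes the screening questions. It does not say that the script is read word for word or that nothing else is said. This stands: the documents show that the script does not match section 5.1, not that candidates are never told about TMS. It does not rescue the sentences in the script that conflict with the protocol.

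- **The wording has a parallel in the protocol.** Section 2.1 says: "TMS is one of the non-invasive brain stimulation tools used to deliver electrical stimuli through the scalp in humans". That explains how an electrical description could arise. It does not support a very weak current for pulses that make a muscle twitch.

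- **The pain statement is hedged.** The script says what the stimulation should do; it does not promise the absence of pain. That is fair, but it still conflicts with the scalp pain reported in section 8.2.1.

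- **The diabetes key may have been lost when the PDF was read.** This cannot be fully excluded. The other six keys survived, which makes it less likely. Even with the key missing, staff know the exclusion criteria (section 3.3.1), and the form has a fail box with space for a reason.

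A reader might also infer that randomised participants will be lost. Section 9.4 removes drop-outs from the analysis, and each is 1/20 = 5% of the sample. The documents do not support that inference. Section 9.4 concerns people who cannot tolerate the glucose or are uncomfortable with the stimulation, and nothing shows that a better script would change their number. Someone who first learns of the procedures at written consent can decline then, before allocation.

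**Conclusion.** Appendix E is wrong as written and conflicts with the protocol on five counts: technique, side effects, number of visits (3 against 4), the glucose drink, and the diabetes item (6 of 7 items keyed). Severity is minor. The likely cost is misinformed candidates and some avoidable screening visits; the documents give no basis for estimating how many.

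Two further readings go beyond the text. One is that consent to the study is invalid. It is not shown to be, because the verbal consent opens only the phone screening and written consent comes before any assessment. The other is that people with diabetes or pre-diabetes will be enrolled. That does not follow either, because eligibility is confirmed on site with a fasting glucose cut-off. The statistical plan is untouched.

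The conclusion assumes that the script is used substantially as printed, that the missing answer is missing from the source document, and that the later consent and eligibility steps are carried out as described.

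**What to change.** Reconcile Appendix E with sections 3.2, 4, 5.1, 5.2, 8.2.1 and 10.1:

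- Replace the weak-current sentence with a short description of TMS and EEG, including the muscle twitch.
- Name the glucose drink and the MRI visit, and give the total as four visits.
- Replace the statements on pain and on the absence of other side effects with the side effects that the protocol itself lists.
- Print the required answer beside the diabetes and pre-diabetes item, consistent with the exclusion in section 3.2.

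The cost is one script revision reviewed by the IRB. Design, sample size and analysis do not change.
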